Visit	Day	Time relative to first drug administration (planned time [h:min])	Approx. time (actual time) [h:min]	Event and comment	$PK_{\text{plasma}}^4$	$PD_{\text{blood}}^4$	Plasma ADA 	Laboratory/ Urinalysis 	Body Temperature	12-lead ECG	ECG monitoring	Vital signs (BP, PR)	Query on adverse events, concomitant therapies 
2	29	672:00	8:00	ambulatory visit	X	X	X						X
	36	840:00	8:00	ambulatory visit	X								X
	43	1008:00	8:00	ambulatory visit	X		X						X
	50	1176:00	8:00	ambulatory visit	X	X							X
	57	1344:00	8:00	ambulatory visit	X		X						
	64	1512:00	8:00	ambulatory visit	X								X
	78	1848:00	8:00	ambulatory visit	X	X	X						X
	92	2184:00	8:00	ambulatory visit	X		X						X
	120 ±3	2856:00	8:00	ambulatory visit	X	X	X						X
	148 ±3	3528:00	8:00	ambulatory visit	X		X						X
3	176 ±3	4200:00	8:00	EOT 	X 	X	X 	X	X	X		X	X

1. Screening with subject information, informed consent as the first measure, includes physical examination, check of vital signs, ECG, safety laboratory (under fasting conditions), drug screening, demographics (including determination of body height and weight, smoking and alcohol history), relevant medical history, concomitant therapy and review of inclusion/exclusion criteria.
2. The time is approximate; procedures are to be performed and completed within 3 h prior to drug administration. Within 3 hours prior to the planned dosing, planned time -2:00 will be used.
3. Laboratory tests (safety laboratory) include clinical chemistry, haematology, coagulation and urinalysis; in addition at screening: serology (HBV, HCV, HIV), and drug screening.
4. PK and PD sampling times may be adapted based on information obtained during trial conduct.
5. Triple ECG
6. Local tolerability inclusive.
7. If several actions are indicated at the same time point, the intake of meals will be the last action.
8. Confirmation of fitness includes physical examination.
9. ADAs samples will be taken at baseline, Day 8, Day 15, Day 22, Day 29, Day 43, Day 57, Day 78, Day 92, Day 120, Day 148 and Day 176 (EOT).
10. The cytokines IL1β, IL6, TNF-α and IFNγ will be collected at baseline, 4h and 24h postdose after each of the 4 single infusions. These samples are only to be analyzed in case of specific adverse events occur that are suggestive for a cytokine release.
11. Only drug screening.

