12. AEs and concomitant therapies will be recorded throughout the trial, but will be specifically asked for at the time points indicated in the [Flow Chart](#) above.
13. EOT (End of trial examination) includes physical examination, body weight, vital signs, ECG, safety laboratory, recording of AEs and concomitant therapies. EOT to be performed not before last PK sampling.
14. Safety laboratory is to be taken within three days prior to study drug administration and can be omitted, if the screening examination is performed between Day -5 to Day -3.
15. First measure after completion of infusion is collection of PK and PD sample
16. In case plasma levels still exceed LOQ additional PK and ADA samples may be collected beyond Day 176

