	57	1344:00	8:00	ambulatory visit	X		X						
	64	1512:00	8:00	ambulatory visit	X								X
	78	1848:00	8:00	ambulatory visit	X	X	X						X
	92	2184:00	8:00	ambulatory visit	X		X						X
	120 ±3	2856:00	8:00	ambulatory visit	X	X	X						X
	148 ±3	3528:00	8:00	ambulatory visit	X		X						X
3	176 ±3	4200:00	8:00	EOT 	X 	X	X 	X	X	X		X	X

1. Screening with subject information, informed consent as the first measure, includes physical examination, check of vital signs, ECG, safety laboratory (under fasting conditions), drug screening, demographics (including determination of body height and weight, smoking and alcohol history), relevant medical history, concomitant therapy and review of inclusion/exclusion criteria.
2. The time is approximate; procedures are to be performed and completed within 3 h prior to drug administration. Within 3 hours prior to the planned dosing, planned time -2:00 will be used.
3. Laboratory tests (safety laboratory) include clinical chemistry, haematology, coagulation and urinalysis; in addition at screening: serology (HBV, HCV, HIV), and drug screening.
4. PK and PD sampling times may be adapted based on information obtained during trial conduct.
5. Triple ECG
6. Local tolerability inclusive.
7. If several actions are indicated at the same time point, the intake of meals will be the last action.
8. Confirmation of fitness includes physical examination.
9. ADA samples will be taken at baseline, Day 8, Day 15, Day 22, Day 29, Day 43, Day 57, Day 78, Day 92, Day 120, Day 148 and Day 176 (EOT).
10. At baseline of each dosing day, cytokines (IL1 $\beta$ , IL6, TNF- $\alpha$  and IFN $\gamma$ ) samples will be collected together with safety lab. Additional cytokines samples IL1 $\beta$ , IL6, TNF- $\alpha$  and IFN $\gamma$  will be collected at 4h and 24h post-dose after each of the 4 single infusions. Cytokines samples are only to be analysed from an individual subject in case of specific adverse events in this subject that are suggestive for a cytokine release. At 4h and 24h post-dose no safety lab needs to be taken.
11. Only drug screening.
12. AEs and concomitant therapies will be recorded throughout the trial, but will be specifically asked for at the time points indicated in the [Flow Chart](#) above.

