Visit	Day	Time relative to first drug administration (planned time [h:min])	Approx. time (actual time) [h:min]	Event and comment	PK blood 	PD blood 	Plasma ADA 	Laboratory/Urinalysis 	Body Temperature	12-lead ECG	ECG monitoring	vital signs (BP, PR)	Query on adverse events, concomitant therapies 
2	36	840:00	8:00	ambulatory visit	X								X
	43	1008:00	8:00	ambulatory visit	X	X	X						X
	57	1344:00	8:00	ambulatory visit	X		X						X
	71	1680:00	8:00	ambulatory visit	X	X	X						X
	92 ±2	2184:00	8:00	ambulatory visit	X		X						X
	120 ±3	2856:00	8:00	ambulatory visit	X	X	X						X
	148 ±3	3528:00	8:00	ambulatory visit	X		X						
3	176 ±3	4200:00	8:00	EOT 	X 	X	X 	X	X	X	X	X	X

1. Screening with subject information, informed consent as the first measure, includes physical examination, check of vital signs, ECG, safety laboratory (under fasting conditions), drug screening, demographics (including determination of body height and weight, smoking and alcohol history), relevant medical history, concomitant therapy and review of inclusion/exclusion criteria.
2. The time is approximate; procedures are to be performed and completed within 3 h prior to drug administration. Within 3 hours prior to the planned dosing, planned time -2:00 will be used.
3. Laboratory tests (safety laboratory) include clinical chemistry, haematology, coagulation and urinalysis; in addition at screening: serology (HBV, HCV, HIV), and drug screening.
4. PK and PD sampling times may be adapted based on information obtained during trial conduct.
5. From Day 1 (predose) to Day 3 (discharge from the unit) ECGs will be recorded as triple ECG.
6. Local tolerability inclusive.
7. If several actions are indicated at the same time point, the intake of meals will be the last action.
8. Confirmation of fitness includes physical examination.
9. ADAs samples will be taken at baseline, Day 8, Day 29, Day 43, Day 57, Day 71, Day 92, Day 120, Day 148 and Day 176 (EOT) after BI 655130 administration.
10. The cytokines IL1β, IL6, TNF-α and IFNγ will be collected at baseline, 4h and 24h postdose. At 4 h there will be only an assessment of cytokines, while at baseline and 24 h cytokines will be determined together with safety lab. The cytokine samples only to be analyzed in case of specific adverse events suggestive for cytokine release.
11. Only drug screening.

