#### 5.2.2.2 Adverse event collection and reporting

##### AEs collection

Upon enrolment into a trial, the subject's baseline condition is assessed (for instance, by documentation of medical history/concomitant diagnoses), and relevant changes from baseline are noted subsequently.

Subjects will be required to report spontaneously any AEs as well as the time of onset, end, and intensity of these events. In addition, each subject will be regularly assessed by the medical staff throughout the clinical trial and whenever the investigator deems necessary. As a minimum, subjects will be questioned for AEs (and concomitant therapies) at the time points indicated in the [Flow Chart](#). Assessment will be made using non-specific questions such as 'How do you feel?'. Specific questions will be asked wherever necessary in order to more precisely describe an AE.

A careful written record of all AEs shall be kept by the investigator in charge of the trial. Records of AEs shall include data on the time of onset, end time, and intensity of the event as well as any treatment or action required for the event and its outcome.

The following must be collected and documented on the appropriate CRF(s) by the investigator:

[figure not shown]
- From signing the informed consent onwards through the residual effect period (REP), until individual subject's end of trial:
  - All AEs (serious and non-serious) and all AESIs.
  - The only exception to this rule are AEs (serious and non-serious) and AESIs in Phase I trials in healthy volunteers, when subjects discontinue from the trial due to screening failures prior to administration of any trial medication. In

Proprietary confidential information © 2017 Boehringer Ingelheim International GmbH or one or more of its affiliated companies

these cases, the subjects' data must be collected at trial site but will not be entered in the CRF or trial database and will not be reported in the CTR.

- After the individual subject's end of trial:

- The investigator does not need to actively monitor the subject for AEs but should only report relevant SAEs and relevant AESIs of which [REDACTED] may become aware of.

The REP for BI 655130, when measurable drug levels or PD effects are still likely to be present after the last administration, is not known at this early stage of development. Therefore, all AEs reported until the end of trial examination will be considered on treatment; please see [Section 7.3.3](#).

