#### **7.3.3 Safety analyses**

Safety will be assessed for the endpoints listed in [Section 5.2.1](#). All treated subjects (that is, all subjects who received at least one dose of study drug), will be included in the safety evaluation. Safety analyses will be descriptive in nature and will be based on BI standards.

Treatments will be compared in a descriptive way. The placebo control group in the safety evaluation will consist of all placebo treated subjects, regardless of the dose group in which they were treated. The active treatment groups will be compared to the placebo group in a descriptive way. Tabulations of frequencies/proportions will be used for the evaluation of categorical (qualitative) data, and tabulations of descriptive statistics will be used to analyse continuous (quantitative) data. Separate listings will be provided for subjects under multiple drug administration and the ones with a single dose of 20 mg/kg.

The analyses will be done by 'treatment at onset'.

Measurements (such as ECG, vital signs, or laboratory parameters) or AEs will be assigned to treatments (see [Section 4.1](#)) based on the actual treatment at the planned time of the measurement or on the recorded time of AE onset (concept of treatment emergent AEs).

Therefore, measurements planned or AEs recorded prior to first intake of trial medication will be assigned to 'screening', those between first trial medication intake until the end of trial visit will be assigned to the treatment period, and those after the end of trial examination will be assigned to 'post-study'. These assignments including the corresponding time intervals will be defined in detail in the TSAP.

Additionally, further treatment intervals (analysing treatments) may be defined in order to provide summary statistics for time intervals, such as combined treatments, on-treatment totals or periods without treatment effects (such as screening and post-study intervals). Adverse events will be coded using the Medical Dictionary for Regulatory Activities (MedDRA). Frequency, intensity and causal relationship of AEs will be tabulated by treatment, primary system organ class and preferred term. SAEs, AESIs (see [Section 5.2.2.1](#)) and other significant AEs (according to ICH E3) will be listed separately.

Laboratory data will be compared to their reference ranges. Values outside the reference range will be flagged. Additionally, differences from baseline will be evaluated.

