6. GENERAL ANALYSIS DEFINITIONS

6.1 TREATMENTS

For basic study information on treatments to be administered, assignments of dose groups, and selection of doses, cf. Section 4 of the CTP.

Subjects were planned to be treated either with

- four intravenous doses of 3 mg/kg, 6 mg/kg, 10 mg/kg or 20 mg/kg body weight of BI 655130 (test treatment)
or
- four intravenous doses of placebo (reference treatment)
or
- a single intravenous dose of 20 mg/kg body weight of BI 655130 (test treatment)
or
- a single intravenous dose of placebo (reference treatment).

All placebo subjects from multiple dose groups will be analysed in one pooled placebo group (i.e. no distinction between multiple dose groups will be made for placebo subjects). Placebo subjects from the single dose group will be analysed separately.

In displays of disposition, demographics and safety, results of statistical analysis for multiple dose groups will be presented side by side with those for the single dose group in the same tables.

For statistical analysis of AEs, safety laboratory data, vital signs and ECG, the following analysis phases are defined for each subject:

Table 6.1: 1 Flow chart of analysis phases for statistical analyses of AEs, safety laboratory data, vital signs and ECG

Study analysis phase	Label	Start (inclusive)	End (exclusive)
Screening	Screening	Date of informed consent	Date/time of first administration of study drug
On-treatment	Placebo MD, Placebo SD, BI 3 mg/kg MD, BI 6 mg/kg MD, BI 10 mg/kg MD, BI 20 mg/kg MD, or BI 20 mg/kg SD, respectively	Date/time of first administration of study drug	12:00 AM on day after subject's trial termination date

CTR Section 15, Appendix 16.1.9.2.8.2 and Appendix 16.1.9.2.8.3 AE displays will present results for the on-treatment phase only.

In CTR Section 15 AE tables (but not in Appendix 16.1.9.2.8.2 and Appendix 16.1.9.2.8.3 AE tables), the following total will be provided in addition:

- **"Total on-trt BI MD"**, defined as the total over all on-treatment phases involving BI multiple dose treatment only, ignoring placebo and single dose BI

CTR Appendix 16.1.9.2.8.1 displays will present results for the screening and on-treatment phases.

More details on the technical implementation of these analyses are provided in the ADS Plan of this TSAP.

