7.8.2 Laboratory data

The analyses of laboratory data will be descriptive in nature and will be based on BI standards (7). If possible, analyses will be based on original values. If multiple reference ranges apply for a parameter (e.g. due to different age groups), analyses will be based on normalised values, which means transforming to a standard unit and a standard reference range.

Descriptive statistics of laboratory values over time and for the difference from baseline (see [Section 6.7](#)) will be provided. Frequency tables of changes between baseline and last value on treatment with respect to the reference range will be presented.

Possibly clinically significant abnormal laboratory values are only those identified either in the Investigator's comments or at the RPM/DBLM at the latest. It is the Investigator's responsibility to decide whether a lab value is clinically significant abnormal or not. Standard or project-specific rules for flagging clinically significant values in an automated manner will not be applied in this study.

Clinically relevant findings in laboratory data will be reported as baseline conditions (at screening) or as AEs (during the trial) if judged clinically relevant by the investigator, and will be analysed as such.

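### The only laboratory shift table the SAP names uses the last on-treatment value, normally Day 176 ±3 for completers, so a shift that arises during dosing and resolves is tabulated as no shift

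*SAP*

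**What the plan says.** - **Shift table.** SAP 7.8.2: "Frequency tables of changes between baseline and last value on treatment with respect to the reference range will be presented". The same section plans descriptive statistics over time and for change from baseline. It refers to the sponsor's laboratory standard (SAP reference 7) and says that no automated rule will flag clinically significant values.
- **End of the on-treatment phase.** SAP Table 6.1: 1, which covers safety laboratory data, ends the phase at "12:00 AM on day after subject's trial termination date". Protocol 7.3.3 agrees: "those between first trial medication intake until the end of trial visit will be assigned to the treatment period".
- **Laboratory at the last visit.** Flow Chart footnote 13: "EOT (End of trial examination) includes physical examination, body weight, vital signs, ECG, safety laboratory". The visit is planned for Day 176 ±3 in every dose group.
- **Early discontinuation.** Protocol 3.3.4.1 asks for a full end-of-trial examination at the time of discontinuation, if possible.
- **Other places where a laboratory value appears.** All individual values are listed and summaries include minimum and maximum (SAP 7). Out-of-range values are flagged (protocol 7.3.3). Values judged clinically relevant are reported as adverse events (SAP 7.8.2).

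**The concern.** The plan assesses safety by describing each active group beside placebo. For laboratory data the natural question is how many subjects in each group left the reference range after dosing began. The named shift table answers a different one: how many were in a different category at their last sample, which for completers comes about five months after the last dose.

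The table also mixes time points, because a subject who stops early may contribute a sample taken close to dosing.

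The SAP takes the other approach for ECG. Section 5.3.2 classifies each subject by the maximum QTc over all on-treatment time points and defines notable findings at any time on treatment. What is at stake is one descriptive count for laboratory tests, which are a further criterion of interest.

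**Working it through.** **1. When the last value is taken.** The Flow Chart puts Day 176 at 4200:00 h after first administration. Check: (176 − 1) × 24 = 4200 h, which agrees.

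- Multiple dose, last dose Day 22: 176 − 22 = 154 days (151–157 with the ±3-day window). The previous scheduled safety laboratory is Day 25, which is 176 − 25 = 151 days earlier.
- Single dose on Day 1: 176 − 1 = 175 days (172–178). The previous scheduled safety laboratory is Day 29, which is 147 days earlier.

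The date is the normal case only. The end-of-trial visit may not precede the last PK sample and so can move later, and an unscheduled repeat could become the last value.

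**2. What the table records.** Take a parameter that is normal at baseline, high from Day 8 to Day 25 and normal on Day 176. Baseline to last is normal to normal, so no shift. If k of 6 active subjects follow this course, the table shows 0/6 for any k. A table of the highest value would show k/6 (1/6 = 16.7%, 2/6 = 33.3%, 3/6 = 50.0%).

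**3. How many planned samples are left out.** Days are read from charts whose columns are partly displaced in the text.

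- 20 mg/kg multiple dose: Days 4, 8, 11, 15, 18, 22, 25 and 176, so the table uses 1 of 8. Footnote 10 places a safety laboratory before each dose and adds "At 4h and 24h post-dose no safety lab needs to be taken".
- 20 mg/kg single dose: Days 2, 4, 8, 22, 29 and 176, so 1 of 6. Footnote 10 covers the Day 2 sample: "while at baseline and 24 h cytokines will be determined together with safety lab".
- 3, 6 and 10 mg/kg: footnote 10 says only that cytokines "will be collected at baseline, 4h and 24h postdose after each of the 4 single infusions". If marks carrying that footnote are not safety laboratories, the table uses 1 of 5 (Days 4, 11, 18, 25, 176). If the predose marks on Days 8, 15 and 22 count, it is 1 of 8. If the 24 h marks count too, those samples have no counterpart in the 20 mg/kg multiple-dose group.

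The days shared by all multiple-dose groups therefore number 5 or 8.

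**4. Chance rate if extremes are used.** The documents give neither the coverage of the reference ranges nor the within-subject correlation, so both are assumed: 95% two-sided ranges, an in-range baseline, and equally correlated normal draws. With Z the subject's shared component, ρ the correlation, c = 1.96 and k draws:

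P(shift upward) = 1 − E[p(Z) · h(Z)^k] / E[p(Z)]

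Here p(Z) is the chance that one draw lies inside the range and h(Z) the chance that it lies below the upper limit. At ρ = 0 this reduces to 1 − 0.975^k, for example 1 − 0.975^8 = 0.183.

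| Draws | One direction, ρ = 0.7 to 0 | Either direction, ρ = 0.7 to 0 |
|---|---|---|
| 1 | 1.8–2.5% | 3.5–5.0% |
| 5 | 6.0–11.9% | 12.0–22.6% |
| 6 | 6.8–14.1% | 13.5–26.5% |
| 8 | 8.0–18.3% | 16.1–33.7% |

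At ρ = 0.9 and 8 draws the rates fall to about 4% and 8%. Expected numbers of unaffected subjects shifting in one direction at 8 draws (ρ = 0.7 to 0) are 6 × 0.080 to 6 × 0.183 = 0.5–1.1 per active group. In the pooled multiple-dose placebo group (4 groups × 2 = 8 subjects) they are 8 × 0.080 to 8 × 0.183 = 0.6–1.5.

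**The case against.** The documents are consistent. They treat everything up to the end-of-trial examination as on treatment because the residual effect period "is not known at this early stage of development", and baseline to last is a sensible display of persistence. With six active subjects per group, a count from a flagged listing is short work. SAP 7.8.2 relies on a sponsor standard that is not available and may supply the count. SAP 6.1 also defers technical detail to an analysis dataset plan that was not supplied, and protocol 7.3.3 allows further treatment intervals. Tables of extremes over many parameters will contain chance shifts.

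Much of this stands. It limits the point to one missing count and makes it conditional on the standard. It does not change what the named table records, and the further intervals are optional, with none set for laboratory data.

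A reader might infer more than the documents support:

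- **That transient abnormalities disappear from the report.** They do not, given the listings, flags, by-visit extremes and adverse event tables.
- **That a reader will have to count by hand.** That holds only if the sponsor standard adds no such table.
- **That the last sample shows the subject free of drug effect.** The residual effect period is unknown, and levels above the quantification limit beyond Day 176 are foreseen. The sample is late, and no more can be said.
- **That escalation decisions are affected.** Protocol 3.1 bases them on review of the laboratory data themselves.

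**Conclusion.** The point holds as a minor one. The one type of shift table named describes late status for completers, 151–157 days after the last multiple dose or 172–178 days after the single dose at the planned visit. Shifts that have returned to the baseline category by then are not counted in it. The loss is the by-group count of subjects who left the range at any time on treatment. No estimate of how many shifts would be missed is possible from the documents.

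The conclusion rests on reading last value on treatment through SAP Table 6.1: 1, and on the sponsor laboratory standard adding no table of its own. The primary endpoint, subjects with drug-related adverse events, is not affected.

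**What to change.** In SAP 7.8.2:

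1. Add shift tables from baseline to the lowest and to the highest on-treatment value per parameter, by treatment, beside the pooled multiple-dose placebo group.
2. For the multiple-dose comparison, use scheduled sampling days common to all multiple-dose groups and state those days, so that active and placebo subjects have the same number of planned draws. This requires settling whether the footnote 10 marks at 3, 6 and 10 mg/kg include a safety laboratory.
3. List separately any subject whose out-of-range value occurs only at an unscheduled or non-shared time point. Otherwise the common-days rule would itself leave some transient shifts uncounted.
4. Show the single-dose group separately, with its own sampling days and its 2 placebo subjects.
5. Keep the last-value table and label it as a return-to-baseline display.

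The cost is two tables and a short listing from data already collected. The drawback is the higher chance rate shown in the working, so the tables should be read only against placebo. With 6 against 8 subjects, only large differences will stand out. If the sponsor standard already provides these tables, one sentence in 7.8.2 saying so is enough.
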